4.4. Efficacy Variables

This section provides more details on the primary, secondary and exploratory endpoints.

However, **no endpoints listed will be formally tested and all p-values are nominal.**

Additional endpoints and analytical methods may be used for exploratory and hypothesis-generating purposes.

4.4.1. Primary Efficacy Variable

The primary endpoint is change from baseline to week 12 in constant work rate exercise endurance time measured from the CWRET (refer to Protocol Section 9.2.2.4 for definition).

4.4.2. Secondary Efficacy Variables

The **secondary** endpoints are:

- Change from baseline to week 12 in pre- and post-exercise (5 seconds, 10 seconds and 20 seconds, respectively) FEV₁ (based on spirometry data; refer to Protocol Section 9.2.2.5 for detailed definition)
- Change from baseline to week 12 in average number of steps walked per day (based on accelerometry data; refer to Protocol Section 9.2.2.1 for detailed definition.)
- Change from baseline to week 12 in total energy expenditure (metabolic equivalents of tasks [METs]) (based on accelerometry data)
- Change from baseline to week 12 in the mean duration of moderate-to-vigorous physical activity (defined as ≥ 3 METs) (based on accelerometry data)

4.4.3. Exploratory Variables

- Change from baseline to week 12 in isotime IC (Note: isotime is defined as the shortest equivalent exercise time achieved)
- Change from baseline to week 12 in perception of dyspnea measured by the Borg Dyspnea Scale at isotime. Refer to Protocol Section 9.2.2.2 for detailed definition.
- Change from baseline to week 12 in perception of leg fatigue measured by the Borg Leg Fatigue Scale at isotime. Refer to Protocol Section 9.2.2.2 for detailed definition.
- Change from baseline to week 12 in end-exercise oxygen consumption (VO₂)
- Change from baseline to week 12 in FeNO, pre- and post-exercise
- Change from baseline to week 12 in forced vital capacity (FVC) pre- and post-exercise
- Change from baseline in FEV1 and FVC at week 4
- Change from baseline to week 12 in the maximal percent fall in post-exercise FEV₁ in patients with exercise-induced asthma (defined as patients who had a $\geq 20\%$ fall in post-exercise FEV₁ from pre-exercise value on the IWRET)
- Change from baseline to week 12 in number of nocturnal awakenings per night due to asthma from patient diary
- Change from baseline in total ACQ-5 score (Asthma Control Questionnaire, 5-question version) at week 12
- Change from baseline to week 12 in total AQLQ(S) score (Asthma Quality of Life Questionnaire Standardized Version). Refer to Protocol Section 9.2.2.2 for detailed definition.
- Proportion of patients responding with an improvement on the Patient Global Impression of Change (PGIC) at weeks 4 and 12. Refer to Protocol Section 9.2.2.4 for detailed definition.
- Proportion of patients responding with no or limited impact on the Patient Global Impression of Impact (PGII) at weeks 4 and 12. Refer to Protocol Section 9.2.2.4 for detailed definition.

4.5. Safety Variables

Patient safety will be assessed through the collection of reported adverse events (AEs), clinical laboratory data, vital signs, ECG and physical exam. Unless otherwise noted, the baseline value is defined as the last available value before the first dose of study treatment.

4.5.1. Adverse Events and Serious Adverse Events

Adverse events and serious adverse events will be collected from the time of informed consent signature and then at each visit until the end of the study. All adverse events are to be coded to a

Preferred Term (PT) and associated primary System Organ Class (SOC) according to the latest available version of Medical Dictionary for Regulatory Activities (MedDRA).

An Adverse Event (AE) is any untoward medical occurrence in a patient administered a study drug which may or may not have a causal relationship with the study drug.

An SAE is any untoward medical occurrence that at any dose:

- Results in **death** – includes all deaths, even those that appear to be completely unrelated to study drug (eg, a car accident in which a patient is a passenger)
- Is **life-threatening** – in the view of the investigator, the patient is at immediate risk of death at the time of the event. This does not include an AE that had it occurred in a more severe form, might have caused death.
- Requires in-patient **hospitalization or prolongation of existing hospitalization**. In-patient hospitalization is defined as hospital admission (any duration) or an emergency room visit for longer than 24 hours. Prolongation of existing hospitalization is defined as a hospital stay that is longer than was originally anticipated for the event or is prolonged due to the development of a new AE as determined by the investigator or treating physician.
- Results in persistent or significant **disability/incapacity** (substantial disruption of one's ability to conduct normal life functions)
- Is a **congenital anomaly/birth defect**
- Is an **important medical event** - Important medical events may not be immediately life-threatening or result in death or hospitalization but may jeopardize the patient or may require intervention to prevent one of the other serious outcomes listed above (eg, intensive treatment in an emergency room or at home for allergic bronchospasm; blood dyscrasias or convulsions that do not result in hospitalization; or development of drug dependency or drug abuse).

The severity of AEs will be graded according to the following scale:

- **Mild:** Does not interfere in a significant manner with the patient normal functioning level. It may be an annoyance. Prescription drugs are not ordinarily needed for relief of symptoms, but may be given because of personality of the patient.
- **Moderate:** Produces some impairment of functioning but is not hazardous to health. It is uncomfortable or an embarrassment. Treatment for symptom may be needed.
- **Severe:** Produces significant impairment of functioning or incapacitation and is a definite hazard to the patient's health. Treatment for symptom may be given and/or patient hospitalized.

The severity of injection site reactions (ISRs) will be graded according to the following scale (semi-colon indicates “or” within description of grade):

- Mild: Pain that does not interfere with activity; mild discomfort to touch; <5 cm of erythema or induration that does not interfere with activity
- Moderate: Pain that requires repeated use of non-narcotic pain reliever >24 hours or interferes with activity; discomfort with movement; 5.1 cm to 10 cm erythema or induration or induration that interferes with activity
- Severe: Pain that requires any use of narcotic pain reliever or that prevents daily activity; significant discomfort at rest; >10 cm erythema or induration; prevents daily activity; requires an emergency room (ER) visit or hospitalization; necrosis or exfoliative dermatitis

4.5.2. Adverse Events of Special Interest

An adverse event of special interest (AESI; serious or non-serious) is one of scientific and medical interest specific to the sponsor's product or program, for which ongoing monitoring and rapid communication by the investigator to the sponsor can be appropriate.

- Anaphylactic reactions
- Systemic or severe hypersensitivity reactions
- Helminthic infections
- Any severe type of Conjunctivitis, Blepharitis
- Keratitis
- Clinically symptomatic eosinophilia (or eosinophilia associated with clinical symptoms)
- Severe injection site reactions lasting for >24 hours

4.5.3. Laboratory Safety Variables

The clinical laboratory data consists of serum chemistry, hematology, and urinalysis. Clinical laboratory values will be converted to standard international (SI) units and grouped by function in summary tables using SI units. The same set of analysis will also be prepared in US units.

Functions are defined as follows:

- Chemistry
- Hematology
- Urinalysis
- Serology

4.5.4. Vital Signs

Vital signs will be collected at time points specified in the study protocol:

- Diastolic Blood Pressure
- Systolic Blood Pressure
- Heart Rate
- Respiratory Rate
- Height
- Weight
- Body Mass Index
- Temperature

4.5.5. ECG

An ECG will be performed just prior to CPET to ensure that the patient does not have a contraindication to CPET. An ECG will be performed throughout the exercise tests as indicated in the schedule of events ([Table 1](#)). The results of the qualifying ECG will be interpreted by a central reading center. All other ECGs will be read locally.

- ECG Mean Heart Rate
- PR Interval, Aggregate
- QRS Duration, Aggregate
- QT Interval, Aggregate
- QTcB Interval, Aggregate
- QTcF Interval, Aggregate
- RR Interval, Aggregate

4.5.6. Physical Examination Variables

A thorough and complete physical examination, including skin, nasal cavities, eyes, ears, respiratory, cardiovascular, gastrointestinal, neurological, lymphatic, and musculoskeletal systems, will be performed at time points according to [Table 1](#).

5. STATISTICAL METHODS

For continuous variables, descriptive statistics will include the following: the number of patients reflected in the calculation (n), mean, standard deviation, first quartile (Q1), median, third quartile (Q3), minimum, and maximum.

For categorical or ordinal data, frequencies and percentages will be displayed for each category.

5.1. Patient Disposition

The following will be provided:

- The total number of screened patients who signed the ICF
- The total number of randomized patients: received a randomization number (as randomized)
- The total number of patients in the SAF
- The total number of patients in the FAS
- The total number of patients who discontinued the study, and the reasons for discontinuation
- The total number of patients who discontinued from study treatment, and the reasons for treatment discontinuation
- Summary table will be provided if applicable

5.2. Demographics and Baseline Characteristics

Demographic and baseline characteristics will be summarized descriptively by treatment group, and by all patients combined based on the FAS population.

Baseline for singular-value assessments, such as measurements from the CWRET, FEV1 and FVC from spirometry, will be the latest valid measurement taken prior to the first administration of study drug.

Baseline for the 7-day average values of measurements from accelerometry is defined as the average of the valid values during the 7 days prior to the first administration of study drug.

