Eligible patients will be randomized 1:1 on day 1 to receive dupilumab or placebo. Background asthma controller medication must remain constant throughout the treatment period. Patients will be asked to wear an accelerometer on their wrist 24 hours/day, 7 days/week for 14 consecutive days prior to visit 3/randomization, and for 14 consecutive days prior to visit 9/end of treatment Visit (except during charging time, bathing, and any other water activities). The CWRET will be performed at baseline and week 12 to assess the change in constant work rate exercise endurance time from baseline, the primary endpoint for the study. In-clinic spirometry will be assessed pre- and post-exercise as part of the CWRET per the schedule of events. Note: The same exercise work rate established at the qualifying run-in CWRET which achieves an exercise time between 3 and 8 minutes must also be applied for the baseline and end of treatment CWRET. Pulmonary ventilation, breathing pattern, gas exchange (all assessed from the respired gases by a metabolic cart), arterial oxygen saturation (assessed by pulse oximetry), ECG parameters, IC, perceived dyspnea and perceived leg fatigue (by Borg Dyspnea and Leg Fatigue Scales, respectively) will be assessed during the CWRET. Details of cardiopulmonary exercise testing procedures including absolute and relative contraindications for performing exercise testing are provided in [Table 2](#) and will also be provided to each site in the CPET laboratory manual. Asthma control, asthma quality of life, nocturnal awakenings due to asthma, and airway inflammation will be assessed at baseline and during the treatment period using the ACQ-5, AQLQ, PGII, and PGIC questionnaires, patient diary and FeNO measurements, respectively. Additional in-clinic spirometry will be performed at week 4 using the same equipment utilized to perform spirometry pre- and post-exercise testing.

Safety, including adverse events, will be assessed throughout the study.

Post-treatment Follow-up Period: (2 Weeks/Visit 10)

All patients will have a follow up visit 2 weeks after completing the treatment period.

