11.4.2. Demography and Baseline Characteristics

Demographic and baseline characteristics will be summarized descriptively by treatment group, and by all patients combined.

Baseline Definitions:

Baseline for singular-value assessments, such as measurements from the CWRET, FEV₁ and FVC from spirometry, will be the latest valid measurement taken prior to the first administration of study drug.

Baseline for the 14-day average values of measurements from accelerometry is defined as the average of the non-missing values during the 14 days prior to the first administration of study drug.

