During the run-in period patients must maintain a stable dose of background asthma controller medication including OCS, if applicable, for at least 4 weeks prior to the baseline visit. Patients will perform a run-in CWRET using a standardized CWRET protocol on an electromagnetically braked cycle ergometer. The CWRET will be performed at 80% of the maximal work rate previously determined from the IWRET. The goal of the run-in CWRET is to determine the individualized work rate the patient can tolerate to achieve an exercise duration time between 3 to 8 minutes, and to familiarize the patient with the test. For those achieving exercise times outside of these limits (ie, <3 to >8 minutes) a second CWRET may be performed after a work rate adjustment by $\pm 10\%$ or 5 W/min, whichever is greater. In rare cases, a third test may need to be performed after a further work rate adjustment to achieve a 3 to 8 minute exercise endurance time. Patients who are unable to achieve an exercise endurance duration between 3 to 8 minutes (180 to 480 seconds) after 3 attempts will be considered screen failures.

At visit 2, patients will be given the accelerometer and instructed on its proper use. Patients will be instructed to wear the accelerometer on their wrist, 24 hours/day, 7 days/week (except during charging time, bathing, and any other water activities) for a total of 3 weeks during the run-in period and record daily how much time spent bathing or swimming, total time charging the device,

physical activity (eg, walking, moderate physical activities, and vigorous physical activities), and nocturnal awakenings due to asthma in the patient diary. The first week is a training period for the patient to become familiar with the accelerometer. The subsequent 2 weeks of daily accelerometry are to obtain the pre-treatment baseline data.

Baseline and Treatment Period (12 Weeks/Visits 3 to 9):

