Eligible patients will be randomized 1:1 on day 1 to receive dupilumab or placebo. Background asthma controller medication must remain constant throughout the treatment period. Patients will be asked to wear an accelerometer on their wrist 24 hours/day, 7 days/week for 14 consecutive days prior to visit 3/randomization, and for 14 consecutive days prior to visit 9/end of treatment Visit (except during charging time, bathing, and any other water activities). The CWRET will be performed at baseline and week 12 to assess the change in constant work rate exercise endurance time from baseline, the primary endpoint for the study. In-clinic spirometry will be assessed pre- and post-exercise as part of the CWRET per the schedule of events. Note: The same exercise work rate established at the qualifying run-in CWRET which achieves an exercise time between 3 and 8 minutes must also be applied for the baseline and end of treatment CWRET. Pulmonary ventilation, breathing pattern, gas exchange (all assessed from the expired gases by a metabolic cart), arterial oxygen saturation (assessed by pulse oximetry), ECG parameters, IC, perceived dyspnea and perceived leg fatigue (by Borg Dyspnea and Leg Fatigue Scales, respectively) will be assessed during the CWRET. Asthma control, asthma quality of life, nocturnal awakenings due to asthma, and airway inflammation will be assessed at baseline and during the treatment period using the ACQ-5, AQLQ, PGII, and PGIC questionnaires, patient diary and FeNO measurements, respectively. Additional in-clinic spirometry will be performed at week 4 using the same equipment utilized to perform spirometry pre- and post-exercise testing.

Safety, including adverse events, will be assessed throughout the study.

Post-treatment Follow-up Period: (2 Weeks/Visit 10)

All patients will have a follow up visit 2 weeks after completing the treatment period.

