5.7.1. Analysis of Primary Efficacy Variable

The primary endpoint of change from baseline in constant work rate exercise endurance time at week 12 will be descriptively summarized.

Please note that the primary endpoint of change from baseline in constant work rate exercise endurance time at week 12 was originally planned to be analyzed using ANCOVA model for the

FAS with treatment group, randomization stratification factor, and relevant baseline measurement as covariates included in the model.

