5.7.2. Analysis of Key Secondary Efficacy Variable

Pre-exercise FEV1 will be assessed within 15 minutes prior to the start of the exercise testing and post-exercise FEV1 will be performed at minutes 5±1, 10±1, and 20±1 post-exercise. Pre-exercise FEV1 and Post-exercise FEV1 will be analyzed descriptively.

Continuous secondary efficacy endpoints that are to be measured by accelerometry will be summarized. 7-day average values of measurements from accelerometry are calculated for baseline and week 12 if days with a wear time of at least 22 hours (accounting for non-wear periods as permissible in protocol) and at least 5 valid days per week are available.

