5.7.3.2. Patient Diary

7-day average values of measurements from patient diary are calculated for baseline and week 12 and will be summarized descriptively if at least 5 valid days per week are available.

Additionally, the same analysis is repeated for patients with at least 4 valid days per week.

- Change from baseline to week 12 in number of nocturnal awakenings per night due to asthma from patient diary

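### The SAP averages accelerometry over 7 days where the protocol defines a 14-day baseline, does not record the change, and does not say which days form the week-12 value

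*SAP*

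**What the plan says.** **Protocol.** Section 11.4.2, like the synopsis, sets the rule: "Baseline for the 14-day average values of measurements from accelerometry is defined as the average of the non-missing values during the 14 days prior" to first dose. Section 6.1 has patients wear the device "for 14 consecutive days prior to visit 3/randomization, and for 14 consecutive days prior to visit 9/end of treatment Visit", after a separate training week. The protocol sets no minimum number of days and does not define a week-12 average.

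**SAP, design section.** Section 2.1 repeats the protocol's collection scheme. Of the run-in it says "The subsequent 2 weeks of daily accelerometry are to obtain the pre-treatment baseline data", and it keeps wear "for 14 consecutive days prior to visit 9/end of treatment Visit".

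**SAP, analysis sections.** Section 5.2 then narrows the window: "Baseline for the 7-day average values of measurements from accelerometry is defined as the average of the valid values during the 7 days prior" to first dose. Section 5.7.2 calculates 7-day averages for baseline and week 12. A valid day needs at least 22 hours of wear after allowing for permitted removal, and each average needs at least 5 valid days per week. No start or end day is given for week 12. Section 6.1 plans no imputation.

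The endpoints affected are daily steps, total energy expenditure and time in moderate-to-vigorous activity, three of the four secondary endpoints in SAP section 4.4.2.

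**The concern.** The SAP disagrees with the protocol, and its section 2.1 disagrees with its own sections 5.2 and 5.7.2. The collection scheme was left at two weeks while the averaging was cut to one.

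The SAP is open about its other departures. It says the primary endpoint "was originally planned to be analyzed using ANCOVA model", and it explains the smaller sample and the loss of formal testing. Nothing comparable is said about the accelerometry window.

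Three things are at stake:

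- **Precision.** Half of the collected days are set aside in a study that has already shrunk from a planned 140 patients to about 40.
- **Reproducibility.** Two programmers could take different 7-day blocks at week 12, or read the weekly minimum as applying to either or both wear weeks.
- **Evaluable patients.** Someone with 4 valid days in the last baseline week and 6 or 7 in the week before has 10 or 11 valid days of 14 but no baseline value. For the exploratory diary endpoint the SAP softens its minimum: "Additionally, the same analysis is repeated for patients with at least 4 valid days per week". The secondary accelerometry endpoints get no such repeat.

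**Working it through.** The plan gives no figure for this choice beyond the day counts, so there is no stated result to reproduce. The sample-size statement concerns exercise endurance time and does not bear on it.

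**What is certain.** Protocol window 14 days, SAP window 7 days: 7 of 14 baseline days are unused.

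**Precision (assumed inputs).** Scale the variance of a single day to 1. Let ICC be the share that lies between patients, ρ the correlation of a patient's underlying level between the two visits, and k the number of valid days averaged, with independent day-to-day noise. Then

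Var(change) = 2·ICC·(1 − ρ) + 2·(1 − ICC)/k.

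| ICC | ρ | k = 7 | k = 14 | Variance ratio | SD ratio |
|---|---|---|---|---|---|
| 0.8 | 0.7 | 0.537 | 0.509 | 1.06 | 1.03 |
| 0.6 | 0.8 | 0.354 | 0.297 | 1.19 | 1.09 |
| 0.4 | 0.9 | 0.251 | 0.166 | 1.52 | 1.23 |

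For the middle row: 2(0.6)(0.2) = 0.240; 2(0.4)/7 = 0.114; 2(0.4)/14 = 0.057. The ratio is 0.354/0.297 = 1.19.

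**Patients (assumed inputs).** Let p be the chance that a day is valid, independent across days. Take the last 7 days as the week-12 block, require a value at both visits, and start from 40 patients. Write A = P(at least 5 of 7), B = P(at least 10 of 14), and J = P(at least 10 of 14 and at least 5 of the last 7).

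- Lost under the SAP rule: 40(1 − A²)
- Lost under 10 of 14: 40(1 − B²)
- Pass 10 of 14 but fail the SAP rule: 40(B² − J²)
- Pass the SAP rule but fail 10 of 14: 40(A² − J²)

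| p | Lost, SAP rule | Lost, 10 of 14 | Lost, 7 of 14 | Pass 10 of 14, fail SAP | Pass SAP, fail 10 of 14 |
|---|---|---|---|---|---|
| 0.95 | 0.3 | 0.03 | 0.0 | 0.3 | 0.02 |
| 0.90 | 2.0 | 0.7 | 0.0 | 1.6 | 0.3 |
| 0.80 | 11.0 | 9.7 | 0.2 | 4.8 | 3.6 |
| 0.70 | 23.3 | 26.3 | 2.5 | 3.6 | 6.7 |

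At p = 0.80: A = 0.852, B = 0.870, J = 0.798, so 40(0.870² − 0.798²) = 4.8.

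**If wear clusters within patients.** Beta-binomial wear with within-patient correlation 0.1 or 0.3 (400,000 simulated patients) gives, per 40 patients at correlation 0.1 / 0.3:

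| Mean validity | Pass 10 of 14, fail SAP | Lost under 7 of 14 |
|---|---|---|
| 0.95 | 0.7 / 0.4 | 0.1 / 1.0 |
| 0.90 | 1.5 / 0.9 | 0.5 / 2.4 |
| 0.80 | 2.6 / 1.4 | 2.6 / 6.0 |

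A 14-day window at a similar required fraction (10 of 14, 71%, as with 5 of 7) saves few patients and can lose more. Only a lower fraction recovers many.

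**The case against.** **The SAP is allowed to change.** Protocol section 11 foresees SAP revision before database lock, and a valid-day rule improves on a protocol definition that had none. That stands as authority to make the change. It does not explain the change, nor reconcile SAP section 2.1 with sections 5.2 and 5.7.2. The SAP's front pages were not available to this check, so the missing record is established for the body only.

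**Week 12 has an obvious reading.** By analogy with baseline it is the last 7 days before visit 9. That is the natural reading, and the calculation above uses it, but it is not written down.

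**The visit window may favour 7 days.** Wear starts at week 10 and visit 9 may fall 3 days early. A patient who starts on day 71 and attends on day 82 has about 11 wear days, so a 14-day window reaches back before wear began. This does little harm if the mean is taken over valid days, because unworn days are simply not valid. The SAP does not offer this as its reason.

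**The size is assumed and patient loss largely cancels.** Both are true. At p = 0.70 the matched 14-day rule loses more patients than the SAP rule. The case for 14 days rests mainly on precision.

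**Everything is descriptive.** Also true. The SAP already reports n with each continuous summary and permits extra exploratory analyses. This limits the weight of the point, but a descriptive endpoint still needs a single definition.

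**Conclusion.** The concern holds. The protocol-to-SAP change, the lack of any reason in the SAP body and the unnamed week-12 days all follow directly from the texts.

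The consequence is modest. On assumed ICC of 0.4 to 0.8 and between-visit correlation of 0.7 to 0.9, with every day valid, the 7-day average raises the standard deviation of change by 3% to 23%, about 9% at the middle values. The effect on evaluable numbers depends on wear behaviour that the documents do not describe, and mostly on the threshold rather than the window. No power or type I error claim is affected.

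The missing record and unnamed week-12 days would by themselves be missing detail. What makes the change worth recommending is that the protocol's own definition uses data already collected and gives a more precise summary of three secondary endpoints in a small study.

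**What to change.** 1. **SAP section 5.2:** define baseline as the mean of all valid days in the 14 days before first dose.
2. **SAP section 5.7.2:** define the week-12 value as the mean of all valid days in the 14 days before visit 9, to match the wear period. Keep the 22-hour valid-day rule with permitted removal.
3. **State one minimum over the 14 days.** Neither document supplies one. At least 7 of 14 is a suggestion: each mean then rests on at least as many days as a full SAP week.
4. **Keep the 7-day, 5-valid-day average as a sensitivity summary.** Name its 7 days at week 12 and report evaluable numbers per arm under both rules.
5. **If the 7-day average stays as the main one,** record the departure from the protocol and the reason, and name the week-12 days.

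The cost is SAP wording and one changed derivation, with no new data. The drawbacks are that means may rest on unequal numbers of days, possibly mostly from one of the two weeks, that 7 of 14 lowers the required fraction from 71% to 50%, and that any wear minimum still selects on wear behaviour.
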